Measures and Data Collection

We will collect data from nine sources. The first three comprise participant assessments that will be completed at baseline, 6, and 12 months.

1. HbA1c. To objectively measure our clinically meaningful primary outcome of change in HbA1c, participants will have their HbA1c measured at a Michigan Medicine lab. The A1c completed as part of the enrollment process to confirm eligibility will also be used as the baseline A1c value. If enrollment is delayed and three or more months lapse between the A1c measure and final enrollment steps, the participant will need to get another A1c test completed to be used for the baseline measure.
2. Weight. Participants will be shipped a digital body weight scale after the participant is fully enrolled. Participants will be given instructions on how to use their scales to weigh themselves (use of scale, time of day, type of clothing) and how to submit a photo of the scale's display of their weight to the study in the secure Way to Health platform. See final section of protocol beginning on page 19 for details on privacy, confidentiality, and security measures. Participants will keep the scale after their study participation ends.
3. Survey. Participants will complete online surveys in the W2H platform at three time points. None of these measures are outcome measures; rather, they describe the participant population, are potential moderators or mediators, or provide insight into the participants' experiences in the study. Survey domains and measures are shown in the table below:

Domain	Survey Month			Measures
	0	6	12	
Demographics	X			Age, gender, race/ethnicity, job, education, household income, whether diagnosed with prediabetes and time since diagnosis, diagnosis of comorbidities, provider clinic and name, people in household, work status
Roles, values, strengths	X	X		Measures from our prior studies ⁶⁷
Physical Activity	X	X	X	International Physical Activity Questionnaire
Eating habits	X	X	X	Rapid Eating Assessment for Participants
Future orientation	X			Consideration of Future Consequences Scale ³³
Health causality orientation	X	X	X	Health Causality Orientations Scale
Autonomous/controlled motivation	X	X	X	Treatment Self-Regulation Questionnaire ¹⁵⁷
Incentive salience		X	X	0 to 10 rating of incentive importance from our prior studies ^{39,41}
Perceived coercion	X	X		Financial Incentive Coercion Assessment Questionnaire ¹⁷²

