Measures taken to protect privacy and confidentiality are described in the *Privacy and Confidentiality Measures* section of this protocol.

Strategies to Maximize Retention and Data Collection. Participants will receive \$50 when they complete each assessment consisting of the online survey, weigh-in, and A1c test. They will also receive email, text messages, and phone calls to remind them to complete these tasks. We used this approach to limit attrition rates to 2% at 12 weeks in our pilot study and to less than 10% at nine months in two previous trials.^{39,41}

Statistical Design

Sample Size

Based on data from previous studies, in the Enhanced Control Arm we anticipate a mean 12-month absolute HbA1c change (defined as the 12-month measure minus the baseline measure) of 0.0%, a mean 12-month absolute HbA1c decrease of 0.2% in both the Financial Incentives Arm and the Tailored Messages Arm, and a mean 12-month absolute HbA1c decrease of 0.4%

in the Combo Arm. Assuming a 0.4% standard deviation for 12-month HbA1c change in each arm and using an α of 0.017 to adjust for three main comparisons, 85 subjects per arm will provide 99% power to detect the difference between the Financial Incentives Plus Tailored Messages and Enhanced Control Arms (H1a), and 80% power to detect differences between the Combo Arm and the Tailored Messages Arm and the Financial Incentives Arm (H1b). With this sample size, we will also be able to detect meaningful differences (Cohen's d of 0.5 or larger) in secondary outcomes of weight, months of engagement in a Diabetes Prevention Program (DPP), months of taking metformin, and months of engagement in a DPP or taking metformin. To account for possible attrition we have conservatively inflated our sample size by 10% and will enroll 380 participants.

Analysis Plans

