Our primary analytic approach will use ordinary least squares (OLS) regression models for continuous outcomes, adjusting for two stratification variables used in randomization (household income and autonomous motivation to prevent diabetes). To assess balance in randomization, we will compare baseline survey measures across arms. Additionally, we expect some missing data on baseline measures and outcomes and will assess the extent and pattern of missingness (e.g., monotone missingness) and predictors of missing outcomes. If we find a baseline measure to be predictive of missing outcome data, we will also adjust for this measure in analyses of outcomes. As an alternative analytic strategy, we will also use mixed-effects models. We will assess for consistency in the results between the two analytic approaches. If more than 10% of the 12-month data are missing, we will also use a multiple imputation strategy in which we will generate ten imputed datasets for missing data using a sequential regression multivariable imputation method, including intervention arms and other baseline variables.¹⁸⁵ The estimates from both the OLS and mixed-effects model analyses using imputed datasets will then be combined using the method of Rubin and Little.¹⁸⁶ All analyses of outcomes will use an intent-to-treat approach and a Bonferroni corrected α of 0.017. Data will be analyzed by a Data Analyst who will be blinded to arm assignment until all primary outcome data have been collected.

Aim 1: Compare the effectiveness of financial incentives plus tailored messages based on SDT principles, financial incentives, and tailored messages based on SDT principles in decreasing hemoglobin A1c, and weight, and in increasing participation in a DPP or use of metformin.

H1a: The mean decrease in HbA1c will be greater in the Combo Arm than in the Enhanced Control Arm.

H1b: The mean decrease in HbA1c will be greater in the Combo Arm than in the Financial Incentives Arm and the Tailored Messages Arm.

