H2d: Effects of the Combo Arm, Financial Incentives Arm, and Tailored Messages Arm on 12-month change in HbA1c will be moderated by income and future orientation.

To test H2a, H2b, and H2c we will use structural equation modeling (SEM), which in a single framework will provide indirect and total effects, and provide joint significance testing, for the factors from our Conceptual Model that we hypothesize will mediate 12-month change in HbA1c. Using SEM, we will examine each mediator separately and also estimate joint models with both hypothesized mediators. In supplementary analyses, we will use latent growth modeling to separately extend this SEM to longitudinal data on six and 12-month change in HbA1c. We expect these longitudinal data models to confirm the findings from SEM, but if the findings differ we will examine the source of any differences.

To test H2d, we will add to the multivariable OLS regression models described under Aim one (but with the Enhanced Control Arm as the reference) interactions between baseline measures of income and future orientation with indicators for the Combo, Financial Incentives, and Tailored Messages Arms. We hypothesize that the effects of arms with financial incentives on 12-month change in HbA1c will be greater among participants with lower incomes and participants who are less future-oriented. In contrast, we hypothesize that the effects of arms with tailored messages will be greater among participants with higher incomes and participants who are more future-oriented. When a hypothesized moderator is found to statistically significantly modify the effects of an arm on 12-month change in HbA1c, we will conduct separate exploratory mediator analyses among the subgroups defined by this moderator because different intervention effects may imply different mechanisms of effects within subgroups. These mediator and moderator analyses will be repeated for each of the secondary outcomes.

Aim 3: Evaluate facilitators of and barriers to scalability, acceptability, and sustainability of financial incentives plus tailored messages based on SDT principles, financial incentives, and tailored messages based on SDT principles. Fundamental to the scalability, acceptability, and sustainability of our approaches for health systems and community organizations are the costs of the approaches we are testing relative to their effects. Thus we will examine costs of each study arm from the perspective of a payer and create standard costs

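### Aim 2 follows a significant moderator with separate mediation analyses in each subgroup, but never estimates or tests whether the indirect effects differ

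*Combined protocol and SAP*

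**What the plan says.** All of this is in Analysis Plans, Aim 2, unless noted.

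- **Mediation method (H2a-H2c):** "we will use structural equation modeling (SEM), which in a single framework will provide indirect and total effects, and provide joint significance testing".
- **Moderation test (H2d):** the Aim 1 regression is extended with "interactions between baseline measures of income and future orientation with indicators for the Combo, Financial Incentives, and Tailored Messages Arms".
- **Trigger:** "When a hypothesized moderator is found to statistically significantly modify the effects of an arm on 12-month change in HbA1c", the follow-up begins.
- **Follow-up:** "we will conduct separate exploratory mediator analyses among the subgroups defined by this moderator because different intervention effects may imply different mechanisms".
- **Repetition:** "These mediator and moderator analyses will be repeated for each of the secondary outcomes". Aim 1 lists four: weight change, months in a DPP, months adherent to metformin, and months with either.
- **Significance level (opening of Analysis Plans):** "All analyses of outcomes will use an intent-to-treat approach and a Bonferroni corrected α of 0.017". Whether this covers the mediation tests is not spelled out, so both 0.05 and 0.017 are used below.

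Future orientation is measured by the "Consideration of Future Consequences Scale" (Measures and Data Collection, survey table), and no cut-point is given for forming groups. Income has three levels for stratified randomization, one of them non-response (Randomization). Aim 2 does not say which levels would form the income subgroups.

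Nowhere does the protocol name a moderated-mediation model, a multigroup equality test, or an interval for the between-subgroup difference in indirect effects.

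**The concern.** The reason given for the follow-up is a comparison between subgroups, but the method yields one mediation result per subgroup and stops. The quantity that answers the question, the difference in indirect effects, is never computed.

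The trigger does not fill the gap. It concerns the total effect, which may differ between subgroups while the pathway through motivation is the same in both.

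Separate fits also cut each analysis to the size of its subgroup, and require a continuous score to be split. Two tests of middling power on the same true effect often disagree by chance. At stake is a statement that, say, lower- and higher-income participants respond through different mechanisms. The Objective says that these analyses will guide refinement of the intervention and its spread to other settings.

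**Working it through.** **1. The plan's own figures.** Sample Size states that "85 subjects per arm will provide 99% power to detect the difference between the Financial Incentives Plus Tailored Messages and Enhanced Control Arms", and 80% for each H1b comparison. Inputs from the same section are SD 0.4, differences 0.4 and 0.2, and α 0.017 (taken as two-sided, z = 2.387).

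- SE = 0.4 × √(2/85) = 0.0614.
- H1a: Φ(0.4/0.0614 − 2.387) > 0.999.
- H1b: Φ(0.2/0.0614 − 2.387) = Φ(0.87) = 0.81.
- Enrolment: 340/0.9 = 378, against 380 planned.

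These reproduce. There is no stated figure for mediation or subgroups.

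**2. Why the trigger is not enough.** In subgroup g, total effect = a_g·b_g + c′_g, where a is arm to mediator, b is mediator to outcome and c′ is the direct effect. The trigger tests the difference in the whole sum. Take a = 0.6 and b = 0.4 in both subgroups, with c′ = 0 in one and 1 SD in the other. The totals are 0.24 and 1.24 SD, while the indirect effect is 0.24 in both.

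**3. Chance of discordant verdicts when the mechanism is identical.** Assumptions, none of them in the protocol: one arm against control with 85 each; subgroups of 42/43 or 17/68 per arm; a in SD units; b standardised; mediation declared when both paths are significant.

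- Power for a: Φ(a√(n/2) − z). Power for b: Φ(b/√(1−b²) × √(2n−3) − z). Their product is the subgroup power p.
- P(exactly one significant) = p₁(1−p₂) + p₂(1−p₁).

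Example with a = 0.5, b = 0.4, α = 0.05 (z = 1.960):

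- n = 42: Φ(2.291 − 1.960) × Φ(3.928 − 1.960) = 0.630 × 0.975 = 0.614. For n = 43, p = 0.626. Discordance = 0.614 × 0.374 + 0.626 × 0.386 = 0.47.
- n = 17: p = 0.210; n = 68: p = 0.829. Discordance = 0.210 × 0.171 + 0.829 × 0.790 = 0.69.

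| a, b | 42/43, α 0.05 | 42/43, α 0.017 | 17/68, α 0.05 | 17/68, α 0.017 |
|---|---|---|---|---|
| 0.2, 0.2 | 13% | 4% | 15% | 6% |
| 0.5, 0.4 | 47% | 49% | 69% | 66% |
| 0.8, 0.4 | 12% | 26% | 56% | 75% |
| 1.0, 0.5 | 1% | 3% | 26% | 44% |

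Simulation with a = 0.4-0.8 and b = 0.4 agrees: about 13-48% (α 0.05) and 29-49% (α 0.017) for the even split, and 47-79% for 17/68. Separate simulation runs differ by a few points, hence the rounded ranges of 13-50% and 45-80%.

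**4. The direct test on the same kind of data.** z = (a₁b₁ − a₂b₂) / √Σ(a_g²·SE(b_g)² + b_g²·SE(a_g)²). With identical mechanisms it is falsely positive in at most about 6% at α 0.05 and 3% at α 0.017.

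**5. After the trigger has fired.** Moderation was built only into the direct path.

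- Direct-effect difference of 0.8 SD: discordance given a significant moderator is 13-66% at 0.05 and 30-74% at 0.017 over the paths and splits tried.
- Difference of 1 SD, even split, a = 0.6, b = 0.4: the trigger fires in about 73%. Discordance is then 40% (0.05) and 49% (0.017), against 3.8% and 0.7% for the direct test.

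**6. Using all four arms to estimate b.** With the other arms at half the a path, discordance is still 9-48% (0.05) and 19-50% (0.017) for an even split, and 43-64% and 49-73% for 17/68. The arm-to-mediator path remains the bottleneck.

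**The case against.** **The plan does not say it will contrast significance.** This is correct. A reader might infer a rule that mechanisms are declared different when mediation is significant in one subgroup only. The protocol states no such rule, and its SEM also yields estimates that could simply be described. What stands is that the rationale is comparative and nothing else is offered for making the comparison.

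**The size depends on assumed paths.** Also correct. A reader might infer that discordance is the usual result, and the figures do not support that. With an even split it stays at or below about half, and it is uncommon at the extremes. Preliminary Studies also hints at a small arm effect on one mediator: baseline autonomous motivation averaged 37.6 on a 6-42 scale, with 18 participants at the maximum. Aim 4 reports that the control arm did best, which makes a strong working mediator in the active arms less plausible. Both point towards the low-discordance end.

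**The trigger may seldom fire.** A 1 SD direct-effect difference equals 1 × 0.4 = 0.4 HbA1c points, the whole assumed Combo-versus-control effect. At 0.5 SD (0.2 points) the trigger fires in about 19% of trials. With conditional discordance of 41-49%, trigger plus discordance is about 0.19 × 0.41 to 0.19 × 0.49, or 8-9%. This lowers the chance of reaching the error, but not the chance of being misled once there.

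**It is labelled exploratory.** True, and no confirmatory claim rests on it. The label limits the consequence but does not make the method answer its question.

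**Conclusion.** The concern holds in a conditional form. The follow-up asks whether mechanisms differ and never estimates the difference, and the trigger cannot stand in for that estimate. This much follows from the text alone.

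The size rests on three assumptions: results are read by significance, the paths are moderate, and the subgroup sizes are as assumed. The protocol documents none of them, including how small the lower-income group would be. Under them, a shared mechanism would look subgroup-specific far more often than under a direct test, most of all with an uneven split.

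The effect is confined to the interpretation of Aim 2. H1a, H1b and the sample size are untouched. The change is worth making because a better analysis is available from the same data.

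**What to change.** Replace the separate subgroup analyses with one moderated-mediation SEM on all participants.

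- **Income:** a multigroup model by stated income levels, saying how non-response is handled.
- **Future orientation:** keep the score continuous and let it interact with the mediation paths.
- **Report:** the difference in indirect effects (for the score, the change in indirect effect across its range) with a bootstrap confidence interval at a stated level.
- **Claim:** say that mechanisms differ only if that interval supports it. Show subgroup indirect effects as descriptive estimates.
- **Scope:** apply the same rule to the secondary outcomes.

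No new data are needed; the cost is plan wording and one model in place of several. There are three downsides. The difference will often be inconclusive at this sample size. The multigroup model does not enlarge a small income group. And because Specific Aims, Aim 4 says that primary and secondary outcomes have been analysed, the change must be labelled as made after those results and kept exploratory. The protocol does not say whether Aim 2 has been run; if it has, the model can be added alongside and the claims limited to what it supports.

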1. If they respond that they *did not* receive a postcard or email that was addressed to them, they will be informed that the study is currently screening and enrolling only those identified that met key study criteria. It will also provide resources for those that are concerned they may have prediabetes and urge them to discuss their concerns with their provider. Study contact information will be provided to allow these individuals to ask any questions they may have.

At least 7 days after the cards and at least 3 days after emails have been sent, a follow-up call will be made to encourage potential participants with a recent A1c in the prediabetes range to consider enrolling in the study. The study team member will follow a script (attached in the IRB section on recruitment) that describes the study. During the call, the study team member will answer any questions the person may have and then offer to ask the screening questions to determine initial eligibility. If the person agrees, the study team member will use a Qualtrics survey to ask and record the screening questions and responses, respectively. Only the studyID will be entered into the Qualtrics survey. If eligible, the study team member will create an account in W2H for the participant and send the participant an email with instructions so that the participant can reset their login password, log into W2H, and continue with the next enrollment step, which is reading the informed consent. No more than three unresponsive call attempts will be made per person, and potential participants will not be mailed or emailed, unsolicited, more than three times (any combination of cards/emails).

W2H web platform. For those who self-enroll by first going to the informational website, potential participants who finish reading the informational website are then taken to the W2H platform and asked to create a unique password-protected online account in W2H and verify their account by entering a code automatically sent to them via text. The W2H platform is a secure, scalable vehicle for conducting RCTs of behavioral interventions that automates enrollment, email and text messaging, delivery of financial incentives, and online survey administration. Drs. [name] and [name] have successfully used the platform in many previous trials. The platform has extensive security measures that are described in detail at the end of this document.

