meaning. Good illustrative statements will be captured verbatim and indicated as such. Notes will be stored in a secure study folder on a departmental shared drive. Interview notes will be coded and analyzed using NVivo software. A code book will be developed beginning with the key domains from the interview guide and using an iterative process among three study staff and PI, with additional codes and subcodes added to account for details that emerged during interviews. The same four individuals will independently code four set of notes and will discuss concordance (Hemmler et al., 2022) to resolve discrepancies in coding via a consensus process. If the study team determines that a high level of consistency in coding had been established, then the sets of notes will be coded independently, with coders applying a “flag for review” code to any sections of text where the coder would like confirmation of a code via team review. If consistency in coding is not established after the group codes four sets of notes, more notes will be coded until consistency in coding is established. The codebook will be revised as needed to reflect new codes that emerge, with notes being recoded as needed. Once coding is complete, the four study team members will independently review key code reports and discuss interpretation of findings. Findings may be used to assist in interpreting study outcomes, improve the program itself, and to identify potential facilitators of and barriers to adoption, implementation, and sustainability. In reports and manuscripts, all data will be deidentified.

9. External controls data. Prior to conducting interviews with the key stakeholders described above as data source #7, we will obtain data that will allow us to share with those interviewed a comparison, between the EUC arm and similar patients who had no intervention, of changes in weight and HbA1c over approximately twelve months. Data will be of patients matching the same initial eligibility criteria that were used for the data pulls for recruitment. Patients will be excluded if they participated in the study, declined to participate after a recruitment call, were unable to reach for recruitment, or were ineligible as determined by screening. Variables provided will be: coded identifier, height, age, sex, race, ethnicity, and both weight and HbA1c with corresponding measurement dates.

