
that will be adjusted to current dollars using medical and pharmaceutical components of the Consumer Price Index. Our cost analysis will also estimate the costs of delivering each study arm, including costs associated with financial incentives and use of the W2H platform.

Sensitivity analyses will be used to examine the impact of using different cost estimates. We will provide stakeholders from Michigan Medicine, BCN, and U-M MHealthy with estimates of the costs of sustaining each approach.

Later in the study, we will develop a detailed plan to evaluate the domains of RE-AIM. Once the plan is developed, we will submit an amendment to IRB for approval.

Aim 4: Compare 12-month changes in HbA1c and weight in the Enhanced Usual Care (EUC) arm to similar patients who received no intervention. Patients receiving no intervention (external controls) will be matched or adjusted for the following characteristics: age, sex, race, ethnicity, and baseline values of BMI, weight and HbA1c. We will use an OLS regression model with 12-month change in HbA1c as the response variable. This model will include an indicator for the EUC (reference is external control), stratification factors, baseline HbA1c values, number of months between two measurements, and any baseline measures that are predictive of missing 12-month data. We will use similar, separate OLS regression models to compare 12-month changes in weight.

Privacy and Confidentiality Measures

Privacy: A potential risk of participation is a breach of a participant's privacy, in which their participation in the research is disclosed to an individual or entity the participant did not wish to have this knowledge. This risk is less serious and lessened in likelihood by collection of informed consent and survey data through the secure W2H web platform.

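### Aim 4 sets no calendar window for the external controls and neither matches nor adjusts for calendar date, so a between-period difference in 12-month change could be mistaken for an effect of Enhanced Usual Care

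*Combined protocol and SAP*

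**What the plan says.** Under Analysis Plans, Aim 4, the external controls are to be "matched or adjusted for the following characteristics: age, sex, race, ethnicity, and baseline values of BMI, weight and HbA1c". The HbA1c model is then specified: "This model will include an indicator for the EUC (reference is external control), stratification factors, baseline HbA1c values", followed by the "number of months between two measurements" and any baseline predictors of missing 12-month data. Weight gets a similar model. The months term records how long the interval was, not when it fell.

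Measures and Data Collection, item 9, defines the control source as "patients matching the same initial eligibility criteria that were used for the data pulls for recruitment". It removes patients who "participated in the study, declined to participate after a recruitment call, were unable to reach for recruitment, or were ineligible as determined by screening". No start or end date for control measurements is given. The extract will, however, hold "both weight and HbA1c with corresponding measurement dates".

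The Recruitment section explains why those exclusions matter. Patients on the pull are mailed or emailed, and then "a follow-up call will be made to encourage potential participants with a recent A1c in the prediabetes range to consider enrolling" in the study. The pull also admits patients with no HbA1c test in the past year. The eligible pool is put at 10,000 or more, against at most 500 consented.

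Specific Aims describes Aim 4 as exploratory, added once the EUC arm was seen to have done best, and meant as context for the staff to be interviewed.

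**The concern.** The Aim 4 model largely repeats the Aim 1 model. In Aim 1 calendar time is balanced because all arms are randomised over the same period. Aim 4 has no randomisation, and nothing in the plan takes over that job.

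The exclusions make the gap more than formal. A patient with an in-range HbA1c who was called would normally end as a participant, a decliner, unreachable or ineligible, and all four groups are removed. Patients with no recent HbA1c at the pull are not targeted for calls and may remain, but their baseline must come from a test on some other date. Both routes could move control baselines away from the months in which EUC participants enrolled.

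If the expected 12-month change differed between the two periods, for instance through new weight or glucose drugs, changed care or a laboratory shift, the EUC coefficient would carry that difference. It could create an apparent benefit or hide a real one. Because the EUC result was known when the aim was written, an unstated control window is also a choice left open after seeing the data.

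**Working it through.** **1. The plan's own figures.** Sample Size gives SD 0.4 for 12-month HbA1c change, 85 analysed per arm and α = 0.017. SE = 0.4 × √(2/85) = 0.0614, and the two-sided critical value is 2.387.

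- Difference 0.2: Φ(0.2/0.0614 − 2.387) = 80.9% (80.1% by noncentral t), against 80% stated.
- Difference 0.4: 99.998%, against 99% stated.

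These reproduce, so SD 0.4 and n = 85 are used below. The plan gives no sample size, power or drift figure for Aim 4.

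**2. Which time effects bias a change score.** Let g(t) be the background HbA1c level at date t. With a 12-month interval, the expected change for a baseline at t is g(t + 12 months) − g(t).

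- Steady linear drift: the same value for every t, so it cancels between groups.
- A repeating seasonal pattern: zero for every t, so it cancels.
- A 12-month change that itself differs between periods: does not cancel and goes into the EUC coefficient.

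Intervals far from 12 months weaken the first two statements. The months term deals with part of that.

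**3. Do the exclusions empty the enrolment period?** Number approached = 500 / yield, where yield (consented per patient approached) is an assumption.

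| Yield | Approached | Left of 10,000 |
|---|---|---|
| 5% | 10,000 | 0 |
| 10% | 5,000 | 5,000 |
| 25% | 2,000 | 8,000 |

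Only a yield near 5% or lower exhausts the pool. The documents give neither the yield nor the recruitment dates, so the question stays open.

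**4. Effect of a between-period difference d, with no true EUC effect.** SE = 0.4 × √(1/85 + 1/(85r)) for r controls per EUC participant. False-positive rate = Φ(d/SE − z) + Φ(−d/SE − z), with z = 1.96 or 2.387. The values of d and r are assumptions. Each cell shows α 0.05 / α 0.017.

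| r | SE | d = 0.02 | d = 0.05 | d = 0.10 |
|---|---|---|---|---|
| 1 | 0.0614 | 6.2% / 2.3% | 12.9% / 5.9% | 37.1% / 22.5% |
| 3 | 0.0501 | 6.8% / 2.6% | 17.0% / 8.3% | 51.4% / 34.8% |
| 10 | 0.0455 | 7.2% / 2.8% | 19.6% / 9.9% | 59.4% / 42.5% |

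**5. Would a date term repair it?** Simulation of 2,000 replicates: 85 EUC baselines spread over years 0–2, 3:1 controls, SD 0.4, and expected 12-month change rising by an assumed 0.05 points per calendar year. By arithmetic, the bias without a date term is 0.05 × (mean EUC year − mean control year).

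| Control baselines | Expected bias | Mean (SD), no date term | Mean (SD), date term |
|---|---|---|---|
| Years 0–2 | 0.05 × (1 − 1) = 0 | 0.001 (0.052) | 0.001 (0.052) |
| Years 0–4 | 0.05 × (1 − 2) = −0.05 | −0.051 (0.052) | −0.001 (0.056) |
| Years 2–4 | 0.05 × (1 − 3) = −0.10 | −0.101 (0.051) | −0.004 (0.091) |

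With overlap the date term costs little. Without overlap it inflates the SD from 0.051 to 0.091, and the estimate rests on extrapolating a straight line.

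**The case against.** The strongest reply is that the documents do not show that the periods differ. A reader might infer that the exclusions push the controls out of the recruitment period. That is not established: the pool is at least 10,000, no count of patients called is given, and several groups could remain as concurrent controls. These are patients not yet called when the target was met, those who opted out from the card or email (the listed exclusion is for declining after a call), and those without a recent HbA1c who were tested later in the same period. This stands, and with fully concurrent controls there is no bias.

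A reader might also infer that any drift over time would be read as an EUC effect. That is too strong, because in a roughly 12-month change score steady drift and same-season effects largely cancel.

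The size also depends on assumptions. Taking 90 EUC participants and unlimited controls gives SE = 0.4/√90 = 0.042 and rates of 12% and 49% at α 0.017 (22% and 66% at 0.05) for differences of 0.05 and 0.10. That is a limiting case, and finite control numbers give less. Nothing in the documents says that differences of this size are usual: 0.10 is half of the 0.2-point difference on which the trial was powered.

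Finally, Aim 4 is exploratory and supplies context for interviews. The plan does not promise to present it as proof of benefit over no intervention. All of this limits the weight of the point. None of it supplies a control window, a date variable or an overlap check.

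**Conclusion.** The omission is real: the plan states no calendar window, does not match on date and has no calendar term, in a non-randomised comparison whose extract already contains the dates. The harm is conditional. It requires control baselines from a different period and a different expected 12-month change in that period.

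Under both conditions a difference of 0.05 or 0.10 points materially raises the false-positive rate, while 0.02 points has little effect. These figures assume SD 0.4 in both groups, 85 EUC participants and 1:1 to 10:1 controls. Both α levels are shown because Aim 4 names none of its own, although the plan's general statement sets 0.017 for outcome analyses. Weight is open to the same bias, but the plan gives no SD from which to size it.

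The point is worth correcting before results are shown to staff. It does not touch the randomised HbA1c comparisons.

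**What to change.** In Analysis Plans, Aim 4, and Measures and Data Collection, item 9:

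- State the window for control baseline dates. Restrict controls to the calendar span of the EUC baselines, or match on baseline date, for example by quarter.
- Where dates overlap, add calendar quarter of the baseline measurement to the HbA1c and weight models.
- Report the distribution of baseline dates in both groups.
- If overlap is poor, do not rely on a date term alone, and state the limitation when the comparison is shown to staff.

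This needs no new data. The likely cost is fewer matched controls. An optional sensitivity analysis could restore patients who could not be reached, drawn from the same months, but item 9 leaves them out of the extract, so it would need a wider data pull.
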